7.2 Statistical Analysis of Primary Endpoint

Persistence at 1 year will be described as the proportion of patients who remain on AS as of their 12 month visit. Specifically, this is defined as the number of patients who are documented as intervention-free at their 12-month visit (Visit 2) divided by the number of patients who chose AS at Visit 1c. Persistence at 2 years will be calculated in a similar manner. Additional analysis will exclude the subjects who were lost to follow-up or died before the 12-month (Visit 2) and 24-month (Visit 4) visits for analysis of the 1-year and 2-year persistence rates respectively. Exact 95% confidence intervals for proportions will be calculated using the F-distribution method $^{(16)}$.

Additionally, the proportion of men who experienced specific outcomes during surveillance, including definitive treatment, physician-reported biopsy findings, exit from the study, and death from all causes will be calculated as a crude proportion. Similar analyses will be conducted to estimate the proportion of patients who persist on AS by NCCN-based risk group (very low, low, and low-intermediate) and by biological risk group defined by NCCN and GPS (probability of favorable pathology \geq 79%, 68-78%, \leq 67%).

Kaplan-Meier methods will be used to estimate time on surveillance free of definitive treatment. Time zero will be defined as the diagnostic biopsy date and time on surveillance free of definitive treatment will be defined as time from diagnostic biopsy to definitive treatment. Patients who withdraw without evidence of definitive treatment or are lost to follow-up will be censored at the time of their last visit and those who died will be censored at the time of death.

The aforementioned methods have been used in prominent AS literature to assess persistence on AS ⁽¹⁷⁾. Because patients lost to follow-up could be drop-outs due to seeking definitive treatment elsewhere, alternative methods that account for informative censoring will be explored to evaluate the consistency of results.

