APPENDIX C: ACTUARIAL LIFE TABLE

Life expectancy for men age 50-82 is presented below. Life expectancy for a given person can be adjusted, using the clinician's assessment of the patient's overall health.* Patients in the best quartile of health (exceptionally healthy) have a 50% longer life expectancy than patients of the same age in the middle two quartiles (of average health). Patients in the worst quartile of health (poor health) have a 50% shorter life expectancy than patients in the middle two quartiles.

The highlighted box in each of the columns represents the age below which all patients in that quartile of health have a life expectancy of greater than 10 years. Patients in the white and yellow boxes are eligible for this study. Patients in the red boxes have a life expectancy of less than 10 years and are not eligible for this study.

Males		Adjusted Life Expectancy** Based on clinician's assessment of overall health		
	Best Quartile Middle Two Quartiles Wo			
Exact age	of Health	of Health	Health	
50	43.5			
50		29.0	14.5	
51	42.2	28.2	14.1	
52	41.0	27.3	13.7	
53	39.7	26.5	13.2	
54	38.5	25.7	12.8	
55	37.3	24.9	12.4	
56	36.1	24.1	12.0	
57	34.9	23.3	11.6	
58	33.7	22.5	11.2	
59	32.5	21.7	10.8	
60	31.4	20.9	10.5	
61	30.2	20.2	10.1	
62	29.1	19.4	9.7	
63	28.0	18.7	9.3	
64	26.9	17.9	9.0	
65	25.8	17.2	8.6	
66	24.7	16.5	8.2	
67	23.7	15.8	7.9	
68	22.6	15.1	7.5	
69	21.6	14.4	7.2	
70	20.6	13.7	6.9	
71	19.6	13.1	6.5	
72	18.7	12.4	6.2	
73	17.7	11.8	5.9	
74	16.8	11.2	5.6	
75	15.9	10.6	5.3	
76	15.1	10.0	5.0	
77	14.2	9.5	4.7	
78	13.4	8.9	4.5	
79	12.6	8.4	4.2	
80	11.9	7.9	4.0	
81	11.1	7.4	3.7	
82	10.4	6.9	3.5	
02	10.7	U.)	5.5	

^{*} NCCN Prostate Cancer Guidelines Version 3.2012.

^{**} Modified from the Social Security Administration Actuarial Life Table, 2007 (http://www.ssa.gov/OACT/STATS/table4c6.html/).

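### Section 7.2 censors deaths in the Kaplan-Meier analysis of treatment-free time on AS, so the curve is not the share still on AS, and no planned summary gives that share while allowing for loss to follow-up

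*Combined protocol and SAP*

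**What the plan says.** Section 7.2 (Statistical Analysis of Primary Endpoint) plans several summaries, and they treat a death in different ways.

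- **Primary proportion.** At one year it is "the number of patients who are documented as intervention-free at their 12-month visit (Visit 2) divided by the number of patients who chose AS", the choice being the one recorded in Visit 1c. The two-year figure is built the same way. A man who died before the visit stays in the denominator and cannot be in the numerator. The text does not say so outright, but he counts as not persisting.
- **Additional proportion.** "Additional analysis will exclude the subjects who were lost to follow-up or died before the 12-month (Visit 2) and 24-month (Visit 4) visits".
- **Crude proportions.** Definitive treatment is among the outcomes listed, and "exit from the study, and death from all causes will be calculated as a crude proportion".
- **Time-to-event analysis.** "Kaplan-Meier methods will be used to estimate time on surveillance free of definitive treatment". The event is treatment alone: "time on surveillance free of definitive treatment will be defined as time from diagnostic biopsy to definitive treatment". For deaths, the rule is that "those who died will be censored at the time of death".

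The section then says that these methods have been used in the AS literature to assess persistence. It also promises to explore methods for informative censoring, but the reason given is that men lost to follow-up may have been treated elsewhere. Death is not mentioned there, and no competing-risk estimator is named anywhere in the section.

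**The concern.** Censoring assumes that the man could still have the event later, unobserved. A man who has died cannot be treated and is not on surveillance. With deaths censored, the curve describes a cohort in which nobody dies. It therefore lies above the proportion alive and untreated, and one minus the curve lies above the proportion actually treated.

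The curve sits under the primary-endpoint heading and is introduced as a persistence method, so its 12- and 24-month values are likely to be quoted as persistence. In that use they are too high, and they will differ from the primary one- and two-year proportions even if nobody is lost. Nothing in the section tells the reader why.

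**Working it through.** **The plan's own figure.** Section 8 states a 90% probability of observing a drop-out rate of 20% or less with 300 men and a true two-year rate of 17%. The exact binomial probability is 90.2% for fewer than 60 drop-outs and 92.6% for 60 or fewer. The normal approximation, Φ(0.03 / √(0.17 × 0.83 / 300)), gives 91.7%. The figure is reproduced, and it does not involve the Kaplan-Meier estimate.

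**Inputs**

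- Two-year treatment risk in the absence of death, p = 17%. This is the Section 8 drop-out figure used as a treatment risk, which is an assumption because Section 8 does not define drop-out. The literature range given there is 20-30%.
- Two-year mortality, m = 1% to 5%. This is also an assumption, since the documents give no mortality rate for men on AS. It is guided by Appendix C ("Life expectancy for men age 50-82 is presented below"). In the average-health column, life expectancy is 17.2 years at 65 and 15.8 at 67. Solving e(65) = (1 − exp(−2μ))/μ + exp(−2μ) × e(67) gives two-year mortality of about 3.6%, or 3.4% if the column is smoothed first. Rounding in the table moves this by about ±0.6 points. Smoothed values are about 1.6% at 55, 2.3% at 60 and 5.3% at 70. Enrolled men may be healthier, hence 1% as the low end.
- Constant hazards, treatment independent of death, no loss to follow-up.

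**Formulas** (24 months, t = 2), with λ = −ln(1 − p)/2 and μ = −ln(1 − m)/2:

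- Kaplan-Meier with deaths censored: exp(−2λ) = 1 − p = 83.0%.
- Alive and untreated: exp(−2(λ + μ)) = (1 − p)(1 − m).
- Gap between the two: (1 − p) × m.
- Cumulative incidence of treatment: λ/(λ + μ) × [1 − exp(−2(λ + μ))], to be compared with 1 − Kaplan-Meier = 17.0%.

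| Two-year mortality | Kaplan-Meier | Alive and untreated | Gap (points) | Cumulative incidence of treatment | Excess of 1 − KM (points) |
|---|---|---|---|---|---|
| 1% | 83.0% | 82.17% | 0.83 | 16.92% | 0.08 |
| 2% | 83.0% | 81.34% | 1.66 | 16.83% | 0.17 |
| 3% | 83.0% | 80.51% | 2.49 | 16.75% | 0.25 |
| 5% | 83.0% | 78.85% | 4.15 | 16.58% | 0.42 |

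At 12 months the gap is √0.83 × (1 − √(1 − m)). That is 0.911 × 0.0050 = 0.5 points at 1% mortality and 0.911 × 0.0253 = 2.3 points at 5%. With a 30% treatment risk, the 24-month gaps run from 0.7 to 3.5 points and the treatment-risk excess from 0.14 to 0.71 points.

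For scale, the 95% half-width of a proportion at n = 300 is 1.96 × √(0.17 × 0.83 / 300), or about 4.3 points.

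**What each planned summary estimates.** Suppose a fraction c of men is lost independently of outcome.

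- The primary proportion estimates (1 − p)(1 − m)(1 − c), because lost men are not documented as intervention-free.
- The additional proportion removes both the lost and the dead. With no loss it is 82.9% to 82.6% for 1% to 5% mortality, close to the Kaplan-Meier value.
- Kaplan-Meier estimates 1 − p.
- The crude proportions make no allowance for incomplete follow-up.

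The target (1 − p)(1 − m) is obtained only when c = 0.

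**The case against.** The strongest reply is that the plan already holds most of what is wanted. The curve is labelled as freedom from treatment, not as the share alive and on AS. As an estimate of time to treatment with death removed, it is valid if death is independent of treatment. If nobody is lost, Aalen-Johansen estimates at 24 months reduce to crude proportions, which are planned, and the primary proportion is itself the share alive and untreated. The bias in treatment risk is far inside the sampling error. The method is also chosen to match published work.

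The mortality inputs may be high as well. The worst-health quartile is ineligible from age 62 under Appendix C. Men must also be alive at Visit 1c, which can fall up to 3 + 4 = 7 months after biopsy, leaving 17 months at risk. At 65 that lowers the gap from 0.83 × 0.036 = 3.0 points to 0.83 × (1 − 0.964^(17/24)) = 2.1 points.

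Much of this stands, and it rules out four stronger readings that a reader might infer:

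- *The curve contradicts the primary proportion.* It does not. They are different quantities, both defined in the section.
- *The gap uses up the 3-point margin between 17% and 20% in Section 8.* That margin concerns the observed drop-out rate. Neither the sample size nor the primary estimate rests on Kaplan-Meier.
- *The overstatement is about 7 points.* That figure (0.83 × 8.6% = 7.1) needs every man to be 75 and in average health, the last eligible age in that column.
- *Risk-group curves would be distorted.* The planned risk-group analysis concerns proportions. No Kaplan-Meier curves by group are specified, and no age difference between groups is documented.

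What does not stand is the claim that nothing is missing. The equivalence with crude proportions fails once men are lost, which the section itself expects. The section's own description also invites the reader to take the curve as persistence.

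**Conclusion.** The point holds as a minor improvement. Read as the share still on AS, the planned 24-month Kaplan-Meier value is too high by about 0.8 to 4.2 points. This rests on assumed two-year mortality of 1% to 5%, a 17% treatment risk, constant hazards and independence of treatment and death. The size depends mainly on mortality, which the documents do not give for this cohort. For the quantity the curve names, the error is negligible. The primary result and the sample size stand as planned. The real gap is that deaths are handled in three ways without a statement of what each result means, and no summary estimates the share alive and on AS while allowing for loss to follow-up.

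**What to change.** In Section 7.2, replace the rule on deaths with wording such as:

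> *Definitive treatment and death before definitive treatment will be analysed as competing events. Aalen-Johansen cumulative incidences of each will be reported with 95% CIs at 12 and 24 months. The probability of being alive and on AS will be reported as 1 minus their sum.*

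Keep the Kaplan-Meier curve as a secondary display for comparison with the AS literature, labelled as not being the share still on AS. State explicitly that a death before the visit counts as not persisting in the primary proportion. Retain the planned informative-censoring work, because Aalen-Johansen also assumes that losses to follow-up are uninformative.

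The cost is a few sentences and standard software output. Death dates are already needed for the planned censoring. The downside is slightly less favourable persistence figures and a main time-to-event result less directly comparable with published curves, which the secondary display covers.

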7.3 Statistical Analysis of the Impact of GPS on the Shared Decision

The primary assessment of the impact of GPS on the shared treatment decision will be performed in the NCCN Low-risk subset of the first 300 patients enrolled in the study with valid GPS results. The analysis will summarize the proportion of patients for whom the treatment recorded on the CRF changed from pre-assay to post-assay along

Protocol Number:	Revision Number:	Effective Date:	Page:
09-023	1.0	Effective Butter	20 of 28

with a two-sided 95% confidence interval (CI). All treatment decision changes, including immediate treatment to AS and vice versa and changes in treatment modality will be characterized. Additional analysis of decision changes will include changes to and from AS only. Similar analysis will also be performed for all 300 patients to estimate an overall change rate across all NCCN risk groups. This analysis will be conducted as soon as 300 patients with valid GPS results and completed pre- and post-assay CRFs have been accrued.

Protocol Number: Revision Number: Effective Date: Page: 21 of 28

7.5 Planned Interim Analyses

Planned Interim analysis will be conducted at two additional time points:

- 1. When all enrolled patients have completed Visit 1C, selection of AS versus immediate treatment will be analyzed. The impact of GPS on shared treatment decision, as described in Section 7.3 will be conducted on all enrolled patients at this time.
- 2. When all enrolled patients have completed Visit 2, persistence on AS at 1 year and quality of life measures will be analyzed.

8. SAMPLE SIZE JUSTIFICATION

The sample size was calculated with the intent of showing a drop-out rate on AS of 20% or less when GPS is incorporated into treatment decisions. A rate of 20-30% is what is reported in the literature ^(17,18). Assuming a true drop-out rate of 17% by 2 years a sample size of 300 patients will be required to achieve 90% probability that the observed drop-out rate will be 20% or less. We expect that if 1200 patients are enrolled, approximately 30%, or 360 of the patients will choose active surveillance and after accounting for patients with insufficient tissue, approximately 300 will be evaluable for the primary endpoint.

Protocol Number:	Revision Number:	Effective Date:	Page:
09-023	1.0	Diceave Date.	22 of 28

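### Section 8 aims at showing AS drop-out of 20% or less, but its 90% figure concerns only the observed rate; the planned exact 95% CI would lie wholly below 20% about 25% of the time at the assumed 17%

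*Combined protocol and SAP*

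**What the plan says.** Section 8 opens with the aim: "The sample size was calculated with the intent of showing a drop-out rate on AS of 20% or less when GPS is incorporated". It places this against a literature rate of 20-30%. The assumed rate behind the sizing is given as "Assuming a true drop-out rate of 17% by 2 years". The criterion built on that assumption reads: "sample size of 300 patients will be required to achieve 90% probability that the observed drop-out rate will be 20% or less". After allowing for the share of men who choose AS and for insufficient tissue, section 8 expects that "approximately 300 will be evaluable for the primary endpoint".

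Section 7.2 defines 1-year persistence as the number documented intervention-free at Visit 2, "divided by the number of patients who chose AS at Visit 1c". For the later time point, "Persistence at 2 years will be calculated in a similar manner". On precision it says: "Exact 95% confidence intervals for proportions will be calculated using the F-distribution".

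Section 8 does not refer to that interval, gives no expected width and does not define drop-out. The documents state no null rate, significance level or CI-based success rule for this endpoint.

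**The concern.** The aim and the sizing criterion in section 8 answer different questions. To show that a rate is 20% or less, the data must make higher rates implausible. An observed rate of 20% or less does not do that, because it is a common result when the true rate sits at or slightly above 20%.

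The 90% stands in the same paragraph as the aim, so a reader can easily take it as the chance of reaching that aim. The 20% benchmark is also the lower edge of the literature range that section 8 quotes, which makes it the natural headline for the 2-year result. At stake is a report that states drop-out of 20% or less as established while the study's own interval still includes higher rates.

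**Working it through.** **Inputs.** From section 8: n = 300 evaluable, assumed true 2-year drop-out 17%, benchmark 20%. From section 7.2: exact 95% CI by the F-distribution method (Clopper-Pearson).

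Two assumptions are needed:
- Drop-out is the complement of section 7.2 persistence.
- The interval is two-sided. Section 7.2 does not say so, but section 7.3 specifies a two-sided 95% CI for its own proportion.

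**Step 1: reproduce the plan's figure.** With X drop-outs distributed Binomial(300, p), an observed rate of 20% or less means X ≤ 60.
- Exact: P(X ≤ 60 | p = 0.17) = 0.9255.
- Strict version: P(X < 60 | p = 0.17) = 0.9025.
- Normal approximation: standard error = √(0.17 × 0.83 / 300) = 0.0217; 0.03 / 0.0217 = 1.38; probability 0.917.

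The stated 90% with 300 men is therefore reproduced, slightly on the conservative side.

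**Step 2: how often the same event occurs at other true rates.**

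| True drop-out | P(X ≤ 60), n = 300 |
|---|---|
| 17% | 0.9255 |
| 20% | 0.5345 |
| 21% | 0.3661 |
| 22% | 0.2233 |

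**Step 3: when the planned interval lies wholly below 20%.** The upper limit for x out of n is the 0.975 quantile of Beta(x + 1, n − x), which is the F-distribution limit in another form.
- x = 46 (15.3%): upper limit 19.92%.
- x = 47 (15.7%): upper limit 20.28%.

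So X ≤ 46 is required, and P(X ≤ 46 | p = 0.17) = 0.2474.

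With a one-sided 95% bound, x = 48 gives 19.90% and x = 49 gives 20.26%. So X ≤ 48 is required, and P(X ≤ 48 | p = 0.17) = 0.3558.

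**Step 4: the most likely result.** The probability of an observed rate of 20% or less with a two-sided CI that still includes 20% is P(47 ≤ X ≤ 60 | p = 0.17) = 0.9255 − 0.2474 = 0.678.

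**Step 5: precision.**
- The assumed result, 51/300 = 17%, has an exact CI of 12.9% to 21.7%.
- The limiting result, 60/300 = 20%, has an exact CI of 15.6% to 25.0%.
- Averaged over Binomial(300, 0.17), the half-width is 4.39 points.

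**Step 6: sensitivity at a true 17%.** Over all n from 280 to 360, the probability that the upper limit is below 20% runs from 20% to 30% two-sided and from 31% to 42% one-sided. At n = 300 a Wilson interval gives 24.7% and a Wald interval 30.0%. None of these is near 90%.

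**The case against.** The strongest reply is that section 8 says what it means. The criterion is openly about the observed rate and is correctly computed. The study is observational, the primary objective in section 2.1 is to assess a rate, and section 7.2 describes a proportion. No rule requires the interval to exclude 20%, so the 25% is the assurance for a criterion the sponsor did not adopt. Section 7.2 also already provides exact CIs, an additional analysis excluding losses and deaths, Kaplan-Meier estimates and exploration of informative censoring. A reader given 51/300 with 12.9-21.7% would see that 20% is not excluded.

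Most of this stands. A reader might infer that 300 is the wrong number, or that the study is underpowered. The documents do not support either: without a declared test there is no power to fall short of, and the stated 90% is right for the stated event. A reader might also infer that the plan will declare success on the point estimate. It contains no such rule.

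The objection to the assumed meaning of drop-out also stands in part. Section 7.2 uses the term in connection with men who may have sought definitive treatment elsewhere. That may be narrower than the complement of persistence, which also counts deaths and every loss to follow-up. The sponsor must say which is meant.

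What does not stand is that the label settles the matter. The paragraph's opening sentence still sets an aim that its criterion cannot meet, and nothing in section 8 tells the reader that the 90% does not refer to that aim.

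**Conclusion.** The point holds as a mismatch between the stated aim and the sizing criterion, not as an error in n or in the 90%. At n = 300 and a true 17%, an observed rate of 20% or less has probability 92.6%, while an exact two-sided 95% CI wholly below 20% has probability about 25% (about 36% for a one-sided 95% bound). The observed-rate event is weak evidence for the aim, since it still occurs 53% of the time at a true 20% and 22% at a true 22%.

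The CI figures rest on about 300 evaluable men, a true rate of 17%, drop-out taken as the complement of section 7.2 persistence, and a two-sided interval. The gap between about 25% and about 90% is too wide for the choice of interval, or any n from 280 to 360, to close. A change to the text is recommended; a change to the design is not.

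**What to change.** Keep about 300 men and make three changes to section 8:

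1. Recast the aim as estimation and give the precision: at a true 2-year drop-out of 17%, the expected exact 95% CI is about 13% to 22%, or about ±4.4 points.
2. State that any conclusion that 2-year drop-out has been shown to be 20% or less will rest on the upper limit of the exact 95% CI already planned in section 7.2. Give its assurance as about 25% at a true 17% (46 or fewer of 300). If the 90% statement is kept, say that it describes the point estimate only.
3. Confirm what drop-out means, in particular whether it is the complement of section 7.2 persistence or refers to definitive treatment, and confirm that the section 7.2 interval is two-sided. Recalculate the assurance if either answer differs from the assumptions here.

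This needs no extra patients, visits or analyses. The cost is a less favourable stated assurance for a 20%-or-less conclusion: about 25%, or about 36% if a one-sided bound is specified. Sizing the study to give that conclusion 90% assurance would take about 1,800 men on AS with a two-sided interval, which is not proposed.

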9. DATA MANAGEMENT

9.1 Data Delivery

Forms capturing Patient Reported Outcomes (PRO) will be completed by patients on paper CRFs, and then entered into the Electronic Data Capture (EDC) system by study personnel, as per study conduct instructions provided by GHI. Other forms will be captured initially in site produced source documentation, and then entered into the EDC system by study personnel. Site personnel will be requested to enter data into the database within five business days of patient visits.

9.2 Data Administration

Study personnel will be trained in study procedures to ensure that all aspects of patient and data management are standardized throughout the duration of the study. All study data should be entered by study personnel using the collection methods designed for this study. Data will be validated in accordance with study-specific Data Management documentation.

